5.7 Toxicities and Dosing Delays/Dose Modifications

Any patient who receives treatment on this protocol will be evaluable for toxicity. Each patient

will be assessed for the development of toxicity except cytokine release syndrome (see below, grading/management per Lee et al. Blood 2014) according to the NCI Common Toxicity Criteria for Adverse Events (CTCAE), version 4.03. Dose adjustments should be made according to the system showing the greatest degree of toxicity. As Blinatumomab is an approved treatment for this indication, reducing or withholding pembrolizumab should be considered as the first option in response to a toxicity prior to adjusting the Blinatumomab dosing.

Adverse events (both non-serious and serious) associated with pembrolizumab exposure may represent an immunologic etiology. These adverse events may occur shortly after the first dose or several months after the last dose of treatment. Pembrolizumab and blinatumomab must be withheld for drug-related toxicities and severe or life-threatening AEs as per Tables below. See Section 5.6.1 in Events of Clinical Interest Guidance Document for additional supportive care guidelines.

All dose adjustments presume that the toxicity is determined by the investigator to be possibly, probably, or definitely related to blinatumomab, pembrolizumab, or both. Withholding the dose and dose adjustments should not occur if toxicity is felt unlikely to be or definitely not related to study blinatumomab, pembrolizumab, or both.

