6.2.1 End of Treatment Visit (Day 38 + 8 days of Cycle 5)

On Day 38 + 8 days of Cycle 5:

Physical exam, performance status, vital signs, weight

Labs: CBC with differential, CMP (sodium, potassium, chloride, bicarbonate, BUN, creatinine, glucose, calcium, total bilirubin, AST, ALT, alkaline phosphatase), direct bilirubin, amylase and lipase

Procedures: Bone marrow aspiration and biopsy. Send for standard histology, flow cytometry, cytogenetics (karyotype and in situ hybridization for previously documented abnormalities only) and quantitative PCR for BCR-ABL1 p190 and/or p210 if previously positive.

MRD assessment: 6-color flow cytometry on bone marrow aspirate on at least 0.5×10^6 mononuclear cells when technically possible. MRD assessment to be done on first pull bone marrow aspirate, redirected bone marrow aspirate should be performed as needed for first pull bone marrow aspirate. MRD samples to be sent to University of Washington for analysis (**Section 7.1.3, Appendix C**).

Imaging: Diagnostic CT chest, abdomen, and pelvis with IV and oral contrast in patients with palpable lymphadenopathy or masses at diagnosis. Patients unable to get contrasted study should get non-contrasted CT scans.

Lumbar puncture with **Methotrexate administration** and CSF studies: Cell count with differential, cytology, and flow cytometry.

Adverse Event Assessment

Concomitant Medications

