6.3 Follow-up Procedures

Patients will be followed for a minimum of 2 years from study entry or until death, whichever occurs first. Patients removed from study for unacceptable adverse events will be followed until resolution or stabilization of the adverse event. Patients taken off study to undergo allogeneic or autologous stem cell transplantation will be censored for relapse and survival as of the date they begin non-protocol therapy. Patients refusing protocol-defined follow-up or lost to follow-up will be censored as to their status on the day of last contact.

Patients will be seen every 3 months for 2 years after completion of therapy. At these visits the following assessment will be performed:

Physical exam, vital signs, weight

Labs: CBC with differential

Concomitant Medications

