8.1 Adverse Event Monitoring

Adverse event data collection and reporting, which are required as part of every clinical trial, are done to ensure the safety of subjects enrolled in the studies as well as those who will enroll in future studies using similar agents. Adverse events are reported in a routine manner at scheduled times during a trial. Additionally, certain adverse events must be reported in an expedited manner to allow for optimal monitoring of patient safety and care.

As far as possible, each adverse event should be evaluated to determine:

- duration (start and end dates)
- severity (grade)
- seriousness
- relationship to study agent
- action taken (i.e., none, study agent modification, medical intervention)
- outcome (i.e., resolved without sequelae, resolved with sequelae, ongoing)

Adverse events monitoring begins after initiation of study treatment and ends 30 days following the last administration of study treatment or study discontinuation/termination, whichever is earlier.

Adverse events may also occur in screened subjects during any pre-allocation baseline period as a result of a protocol-specified intervention, including washout or discontinuation of usual therapy, diet, placebo treatment or a procedure.

Progression of the cancer under study is not considered an adverse event unless it is considered to be drug related by the investigator.

All adverse events will be recorded from the time the consent form is signed through 30 days following cessation of treatment and at each examination on the Adverse Event case report forms/worksheets. The reporting timeframe for adverse events meeting any serious criteria is described in **Section 8.3**.

All patients experiencing an adverse event, regardless of its relationship to study drug {or at least possibly related to the drug}, will be monitored until:

- the adverse event resolves or the symptoms or signs that constitute the adverse event return to baseline;
- any clinically significant abnormal laboratory values have returned to baseline;
- there is a satisfactory explanation other than the study drug for the changes observed; or
- death

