Any serious adverse event, or follow up to a serious adverse event, including death due to any cause other than progression of the cancer under study that occurs to any subject from the time the consent is signed through 90 days following cessation of treatment, or the initiation of new anti-cancer therapy, whichever is earlier, whether or not related to Merck or Amgen product, must be reported within 24 hours to the Sponsor and within 2 working days to Merck Global Safety and Amgen.

Non-serious Events of Clinical Interest will be forwarded to Merck Global Safety and Amgen and will be handled in the same manner as SAEs.

Additionally, any serious adverse event, considered by an investigator who is a qualified physician to be related to Merck or Amgen product that is brought to the attention of the investigator at any time outside of the time period specified in the previous paragraph also must be reported immediately to the Sponsor, Amgen and to Merck.

SAE reports and any other relevant safety information are to be forwarded to the Merck Global Safety [contact]

SAE reports and any other relevant safety information are to be forwarded to the Amegen SAE [contact]

A copy of all 15 Day Reports and Annual Progress Reports is submitted as required by FDA, European Union (EU), Pharmaceutical and Medical Devices agency (PMDA) or other local regulators. Investigators will cross reference this submission according to local regulations to the Merck Investigational Compound Number (IND, CSA, etc.) at the time of submission. Additionally investigators will submit a copy of these reports to Merck & Co., Inc. (Attn: Worldwide Product Safety; [contact]) at the time of submission to FDA.

All subjects with serious adverse events must be followed up for outcome.

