8.8.1.2 Events of Clinical Interest

Selected non-serious and serious adverse events are also known as Events of Clinical Interest (ECI) and must be recorded as such on the Adverse Event case report forms/worksheets and reported within 24 hours to the Sponsor and within 2 working days to:

Merck Global Safety
Attn: Worldwide Product Safety
[contact]

Events of clinical interest for this trial include:

1. An overdose of Merck product, as defined in Section 8.6 - Definition of an Overdose for This Protocol and Reporting of Overdose to the Sponsor, that is not associated with clinical symptoms or abnormal laboratory results.

2. An elevated AST or ALT lab value that is greater than or equal to 3X the upper limit of normal and an elevated total bilirubin lab value that is greater than or equal to 2X the upper limit of normal and, at the same time, an alkaline phosphatase lab value that is less than 2X the upper limit of normal, as determined by way of protocol-specified laboratory testing or unscheduled laboratory testing.*

*Note: These criteria are based upon available regulatory guidance documents. The purpose of the criteria is to specify a threshold of abnormal hepatic tests that may require an additional evaluation for an underlying etiology. The trial site guidance for assessment and follow up of these criteria can be found in the Investigator Trial File Binder (or equivalent).

1. Additional adverse events:

A separate guidance document has been provided entitled “Event of Clinical Interest Guidance Document” (previously entitled, “Event of Clinical Interest and Immune-Related Adverse Event Guidance Document”). This document can be found in Appendix G and provides guidance regarding identification, evaluation and management of ECIs and irAEs.

ECIs (both non-serious and serious adverse events) identified in this guidance document from the date of first dose through 90 days following cessation of treatment, or 30 days after the initiation of a new anticancer therapy, whichever is earlier, need to be reported within 24 hours to the Sponsor and within 2 working days to Merck Global Safety regardless of attribution to study treatment, consistent with standard SAE reporting guidelines.

Merck Global Safety
Attn: Worldwide Product Safety
[contact]

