Subjects should be assessed for possible ECIs prior to each dose. Lab results should be evaluated and subjects should be asked for signs and symptoms suggestive of an immune-related event. Subjects who develop an ECI thought to be immune-related should have additional testing to rule out other etiologic causes. If lab results or symptoms indicate a possible immune-related ECI, then additional testing should be performed to rule out other etiologic causes. If no other cause is found, then it is assumed to be immune-related.

C. The UCSD Human Research Protections Program (HRPP) and Moores Cancer Center Data and Safety Monitoring Board (DSMB) must be notified within 10 business days of “any unanticipated problems involving risk to subjects or others” (UPR).

The following events meet the definition of UPR:

1. Any serious event (injuries, side effects, deaths or other problems), which in the opinion of the Principal Investigator was unanticipated, involved risk to subjects or others, and was possibly related to the research procedures.
2. Any serious accidental or unintentional change to the IRB-approved protocol that alters the level of risk.
3. Any deviation from the protocol taken without prior IRB review to eliminate apparent immediate hazard to a research subject.
4. Any new information (e.g., publication, safety monitoring report, updated

sponsor safety report), interim result or other finding that indicates an unexpected change to the risk/benefit ratio for the research.

5. Any breach in confidentiality that may involve risk to the subject or others.
6. Any complaint of a subject that indicates an unanticipated risk or that cannot be resolved by the Principal Investigator.

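### For a five-cycle completer the last scheduled AE check is 2–10 days after the last pembrolizumab dose, leaving 80–88 days of the 90-day ECI window without scheduled ascertainment

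*Combined protocol and SAP*

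**What the plan says.** **Expected timing.** Section 5.7 treats AEs after pembrolizumab, serious and non-serious, as possibly immunologic, and says: "These adverse events may occur shortly after the first dose or several months after the last dose of treatment".

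**Reporting duties**
- ECIs, serious or not, are reportable from the first dose "through 90 days following cessation of treatment, or 30 days after the initiation of a new anticancer therapy, whichever is earlier" (Section 8.8.1.2). The Overview of Appendix G adds any Grade 3 or higher event that the investigator considers immune-related, whether or not its term is in Table 1.
- Serious AEs are reportable "from the time the consent is signed through 90 days following cessation of treatment, or the initiation of new anti-cancer therapy, whichever is earlier" (Section 8.8.1.1). Serious events judged related to either drug remain reportable with no time limit.
- For all other AEs, Section 8.1 says that monitoring "ends 30 days following the last administration of study treatment or study discontinuation/termination, whichever is earlier". It also says that recording runs from consent "through 30 days following cessation of treatment and at each examination on the Adverse Event case report forms/worksheets".

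**Scheduled checks**
- ECI checks are tied to dosing: "Subjects should be assessed for possible ECIs prior to each dose" (Section 8.8.1.2).
- The last visit that lists an AE assessment is the end-of-treatment visit, Cycle 5 Day 38 + 8 days (Section 6.2.1).
- Section 6.3 says: "Patients will be seen every 3 months for 2 years after completion of therapy. At these visits the following assessment will be performed". The list that follows is physical exam, vital signs, weight, CBC with differential and concomitant medications.
- In the schedule of events, the Adverse Events row stops at end of treatment. The Concomitant Medications row just below it is marked for follow-up and relapse.

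**The concern.** The plan expects immune events months after the last dose and sets a 90-day duty to report ECIs. A duty to report is not a means of finding the event. Once dosing stops, the dose-linked ECI checks stop too, and the only scheduled contacts are quarterly visits with no AE question. A patient with a new non-serious immune event in that time comes to notice only through an unscheduled contact, or through a site that chooses to ask.

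The safety description of a new combination is at stake. Safety and tolerability is a secondary objective (Section 2.2.7). If sites differ in whether they ask, a reader of the results cannot tell whether late immune events were absent or were not looked for.

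**Working it through.** The plan states no figure for this interval, so it is built from the schedule for a patient who completes five cycles without delay.

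**Inputs**
- Cycle length 42 days; pembrolizumab on Days 15 and 36 of each cycle (Section 5.1.3).
- End-of-treatment visit on Cycle 5 Day 38 to 46 (Section 6.2.1).
- Quarterly visits after completion of therapy (Section 6.3). Three calendar months are 89–92 days. The text does not say whether they run from the last dose or from the end-of-treatment visit, so both are shown.
- Windows of 30 days (Section 8.1) and 90 days (Section 8.8.1.2), counted here from the last pembrolizumab dose.

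**Study days**
- Last pembrolizumab dose: 4 × 42 + 36 = Day 204.
- End-of-treatment visit: 4 × 42 + 38 = Day 206 to 4 × 42 + 46 = Day 214.
- Last scheduled AE check after the last dose: 206 − 204 = 2 to 214 − 204 = 10 days.
- 30-day window closes: 204 + 30 = Day 234. Left after the end-of-treatment visit: 234 − 214 = 20 to 234 − 206 = 28 days.
- 90-day window closes: 204 + 90 = Day 294. Left after the end-of-treatment visit: 294 − 214 = 80 to 294 − 206 = 88 days.

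**First quarterly visit**
- Counted from the last dose: 204 + 89 = Day 293 to 204 + 92 = Day 296.
- Counted from the end-of-treatment visit: 206 + 89 = Day 295 to 214 + 92 = Day 306.
- It therefore falls between 1 day before and 12 days after the ECI window closes (293 − 294 = −1; 306 − 294 = 12). Either way, it lists no AE item.
- Time from the end-of-treatment visit with no scheduled contact: 293 − 214 = 79 to 296 − 206 = 90 days on the first count, 89–92 days on the second, so 79–92 days overall.

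**How many patients and events**
- Only patients in CR/CRh after two cycles go on to five cycles (Section 5.1.3), so expected responders are a ceiling on expected completers. At the 29% null rate, 0.29 × 24 = 6.96, about 7. At the 54% target rate, 0.54 × 24 = 12.96, about 13. Transplant lowers both.
- The documents give no late-onset rate. Assume that 2% to 10% of completers have one late non-serious immune event of Grade 2 or higher. Expected events: 7 × 0.02 = 0.14 to 13 × 0.10 = 1.3.

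**The case against.** The strongest reply is that the plan already has a tiered system. All AEs are covered to 30 days, ECIs and serious AEs to 90 days, and related serious AEs indefinitely. An ECI with onset inside 90 days stays reportable even if found later. Events already known are followed until they resolve or stabilise (Sections 5.9 and 8.1). A shorter window for less serious events is a legitimate choice, and the sentence in Section 5.7 is background, not a promise of surveillance. This stands, and it rules out one inference a reader might draw: that safety capture ends 2–10 days after the last dose. Only scheduled checking ends there.

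The second reply is that other text fills the gap.
- Section 6.2 has AEs collected without interruption while the patient is on study, and Section 6.6 separates leaving treatment from leaving the study. But the line sits under procedures during treatment.
- Section 8.1 mentions recording at each examination, and Section 6.1.2 counts any change from screening as an AE. Quarterly visits include an examination. But Section 8.1 also ends monitoring at 30 days, and the schedule cell is blank.
- The two-weekly AE form update (Section 11.6) prompts the site but is not a patient contact.
- A new drug on the concomitant medication list is an indirect sign at best, and Section 6.1.5 generally stops recording medications 28 days after the last dose.

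These passages allow a site to record late events. They do not clearly require it to look for them.

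The third reply is size: about one event at most under an assumed rate, in a 24-patient single-arm study. That is right and limits the weight of the point.

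**Conclusion.** The point holds as a minor mismatch between what the plan expects and requires and what it schedules. Following the schedule as written, 80–88 days of the 90-day ECI window have no planned ascertainment, and late non-serious immune events can be under-recorded or recorded unevenly between sites. The day counts assume no treatment delay and windows counted from the last pembrolizumab dose. The 0.1–1.3 events rest on an assumed rate. No primary result or stopping rule depends on this.

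Two stronger readings are not supported.
- A reader might infer that the safety endpoint in Section 3.2.7 is unusable because its treatment-emergent window is unstated. That is missing detail: the 30 days in Section 8.1 are the natural default, and events after 30 days then fall outside the endpoint.
- A reader might infer from the last scheduled TSH/free T4, on Cycle 5 Day 1, that thyroid monitoring is deficient. Appendix G already calls for testing when clinically indicated, and no figure in the documents shows what extra tests would find.

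**What to change.** - Add to Section 6.3 and to the follow-up column of the schedule: *At each 3-month visit record any new or ongoing immune-related AE/ECI since the last contact, with onset date, grade, attribution, and date of any transplant or new therapy.*
- Amend Section 8.1 to allow this case-report-form recording after 30 days.
- Leave the expedited-reporting windows in Sections 8.8.1.1 and 8.8.1.2 unchanged.
- Tabulate events after 30 days separately, with those after transplant or new therapy in their own row.
- Optional: TSH/free T4 on blood draws already scheduled.

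The cost is one question and a form page at visits already held, with modest data entry. Some late events will be of unclear cause, and a few more ECIs with onset inside 90 days may surface and need the report already required. The change does not shorten the 79–92 days between contacts. Events in that interval would be captured by recall at about three months, which serves the safety description but not early detection.

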5.7.1 Management of non-Hematologic Toxicities

As Blinatumomab is an approved treatment for this indication, reducing or withholding pembrolizumab should be considered as the first option in response to a toxicity prior to adjusting the Blinatumomab dosing.

Any Grade 3 or severe AE that recurs should lead to permanent discontinuation of pembrolizumab, as should any persistent grade 2 or 3 AE (excluding endocrinopathies) that do not recover to grade 1 within 12 weeks of the last dose of pembrolizumab.

Cytokine Release Syndrome	Management for Blinatumomab	Management for Pembrolizumab
Grade 1 -Fever -Constitutional symptoms	Continue infusion. Vigilant supportive care. Assess for infection.	No change in dose. Patient should be admitted for subsequent pembrolizumab dose given in combination with blinatumomab and monitored for at least 72 hours after pembrolizumab administration.
Grade 2 -Hypotension responsive to fluids or one low dose pressor** -Hypoxia: reponds to <40% O ₂ -Organ toxicity: Grade 2	Continue infusion. Vigilant supportive care. Assess for infection.	No change in dose. Patient should be admitted for subsequent pembrolizumab dose given in combination with blinatumomab and monitored for at least 72 hours after pembrolizumab administration.
Grade 3 -Hypotension requiring multiple pressors or high dose pressors** -Hypoxia requiring ≥40% O ₂	Withhold* until resolved then resume blinatumomab at 9 mcg/day. Escalate to 28 mcg/day after 7 days if the toxicity does not recur.	Stop Infusion. Additional appropriate medical therapy may include but is not limited to: IV fluids

Cytokine Release Syndrome	Management for Blinatumomab	Management for Pembrolizumab
-Organ toxicity: Grade 3 or Grade 4 transaminitis	Vigilant supportive care. Assess for infection. Consider administration of corticosteroids and/or tocilizumab.	Antihistamines NSAIDS Acetaminophen Narcotics Oxygen Vasopressors Corticosteroids Tocilizumab Increase monitoring of vital signs as medically indicated until the subject is deemed medically stable in the opinion of the investigator. Hospitalization may be indicated. Subject is permanently discontinued from further trial treatment administration.
Grade 4 -Mechanical ventilation -Organ toxicity: Grade 4 excluding transaminitis	Off protocol therapy. Vigilant supportive care. Assess for infection. Consider administration of corticosteroids and/or tocilizumab..	Off protocol therapy. Vigilant supportive care. Assess for infection. Consider administration of corticosteroids and/or tocilizumab..

*Patients requiring a delay of blinatumomab >14 days should go off protocol therapy.
 
**High-dose pressors include the following administered for ≥3 hours: norepinephrine ≥20 mcg/min, dopamine ≥10 mcg/kg/min, phenylephrine ≥200 mcg/min, epinephrine ≥10 mcg/min, if on vasopressin: vasopressin + norepinephrine equivalent of ≥10 mcg/min, if on combination of vasopressors: norepinephrine equivalent ≥20 mcg/min. NOREPINEPHRINE EQUIVALENT DOSE = [norepinephrine (mcg/min)] + [dopamine (mcg/kg/min)/2] + [epinephrine (mcg/min)] + [phenylephrine (mcg/min)/10]/
		

Neurologic Toxicity	Management for Blinatumomab	Management for Pembrolizumab
Grade 1 or 2	Continue infusion.	No change in dose.
Grade 3	Withhold* until < Grade 2 for 3 days then resume blinatumomab at 9 mcg/day. Escalate to 28 mcg/day after 7 days if the toxicity does not recur. If the toxicity occurred at 9 mcg/day or takes more than 7 days to improve to <Grade 2 then patient goes off protocol therapy.	Withhold* until < Grade 2 then resume at same dose. Missed doses should be given as close to missed scheduled dose as possible. Subsequent doses are given every 3 weeks.
Grade 4	Off protocol therapy	Off protocol therapy
Seizure, Grade 1 or 2	Withhold* until resolved and institute anticonvulsant prophylaxis (neurology consultation)	Withhold until resolved then resume at same dose. Missed doses should be given as close to

Neurologic Toxicity	Management for Blinatumomab	Management for Pembrolizumab
	recommended) then resume blinatumomab at 9 mcg/day. Escalate to 28 mcg/day after 7 days if the toxicity does not recur.	missed scheduled dose as possible. Subsequent doses are given every 3 weeks until completion of planned cycles of therapy.
Seizure, Grade 3 or 4 or recurrent Grade 1 or 2	Off protocol therapy.	Off protocol therapy.
*Patients requiring a delay of blinatumomab >14 days should go off protocol therapy.		

Infusion Reactions	Management for Blinatumomab	Management for Pembrolizumab
≤ Grade 1	Refer to CRS section above.	Increase monitoring of vital signs as needed until clinical stability confirmed. No change in dose.
Grade 2	Refer to CRS section above.	
Stop Infusion and monitor symptoms.
 
Additional appropriate medical therapy may include but is not limited to:
 
 IV fluids Antihistamines NSAIDS Acetaminophen Narcotics 
Increase monitoring of vital signs as medically indicated until the subject is deemed medically stable in the opinion of the investigator.
 
If symptoms resolve within one hour of stopping drug infusion, the infusion may be restarted at 50% of the original infusion rate (e.g., from 100 mL/hr to 50 mL/hr). Otherwise dosing will be held until symptoms resolve and the subject should be premedicated for the next scheduled dose.
 
Withhold until ≤ Grade 1.
 
Premedicate subsequent administration with hydrocortisone 100 mg IV once, diphenhydramine 50 mg IV or per oral (or equivalent alternate antihistamine), Tylenol 650 mg per oral.
 
Subjects who develop Grade 2 toxicity despite adequate premedication permanently discontinue pembrolizumab.

Grade 3
	
Refer to CRS section above.
	
Stop Infusion. Additional appropriate medical therapy may include but is not limited to: IV fluids Antihistamines NSAIDS Acetaminophen Narcotics Oxygen Pressors Corticosteroids Epinephrine
 
Increase monitoring of vital signs as medically indicated until the subject is deemed medically stable in the opinion of the investigator. Hospitalization may be indicated.
 
Subject is permanently discontinued from further trial treatment administration.

Grade 4
	
Refer to CRS section above.
	
Stop Infusion. Additional appropriate medical therapy may include but is not limited to: IV fluids Antihistamines NSAIDS Acetaminophen Narcotics Oxygen Pressors Corticosteroids Epinephrine
 
Increase monitoring of vital signs as medically indicated until the subject is deemed medically stable in the opinion of the investigator. Hospitalization may be indicated.
 
Subject is permanently discontinued from further trial treatment administration.

*Patients requiring a delay of blinatumomab >14 days due to toxicity should go off protocol therapy. Appropriate resuscitation equipment should be available in the room and a physician readily available during the period of drug administration.
		

Pneumonitis	Management for Blinatumomab	Management for Pembrolizumab
≤ Grade 1	No change in dose	No change in dose.
Grade 2	No change in dose.	
Withhold pembrolizumab.
 
Start prednisone 1-2 mg/kg oral daily with taper over at least 4 weeks after resolution to ≤ Grade 1. If pneumonitis recurs at Grade 2 or higher despite corticosteroids then permanently discontinue pembrolizumab.
 
Restart when ≤ Grade 1. Missed doses are not made up.

Grade 3	
Withhold* until resolved to ≤ Grade 1 then resume blinatumomab at 9 mcg/day. Escalate to 28 mcg/day after 7 days if the toxicity does not recur. If pneumonitis recurs then permanently discontinue blinatumomab.
	
Start prednisone 1-2 mg/kg oral daily with taper over at least 4 weeks after resolution to ≤ Grade 1.
 
Administer additional anti-inflammatory measures, as needed. Add prophylactic antibiotics for opportunistic infections in the case of prolonged steroid administration.
 
Discontinue pembrolizumab permanently.

Grade 4	Permanently discontinue blinatumomab.	
Start prednisone 1-2 mg/kg oral daily with taper over at least 4 weeks after resolution to ≤ Grade 1. Administer additional anti-inflammatory measures, as needed. Add prophylactic antibiotics for opportunistic infections in the case of prolonged steroid administration.
 
Discontinue pembrolizumab permanently.

*Patients requiring a delay of blinatumomab >14 days due to toxicity should go off protocol therapy.		

Diarrhea/Colitis	Management for Blinatumomab	Management for Pembrolizumab

General Management: All subjects who experience diarrhea/colitis should be advised to drink liberal quantities of clear fluids. If sufficient oral fluid intake is not feasible, fluid and electrolytes should be substituted via IV infusion. Anti-motility agents may be administered per institutional standard of care. For Grade 2 or higher diarrhea/colitis thought related to study drug(s), gastroenterology consultation for colonoscopic evaluation with biopsies recommended to guide treatment.
		
≤ Grade 1	No change in dose	No change in dose
Grade 2	No change in dose	
Withhold pembrolizumab.
 
Start prednisone 1-2 mg/kg oral daily with taper over at least 4 weeks after resolution to ≤ Grade 1.
 
Restart pembrolizumab when ≤ Grade 1. Missed doses are not made up.

Grade 3	
Withhold* until resolved to ≤ Grade 1 then resume blinatumomab at 9 mcg/day. Escalate to 28 mcg/day after 7 days if the toxicity does not recur. If diarrhea/colitis recurs then permanently discontinue blinatumomab.
	
Start prednisone 1-2 mg/kg oral daily with taper over at least 4 weeks after resolution to ≤ Grade 1.
 
Withhold pembrolizumab until ≤ Grade 1. Missed doses are not made up.
 
If colitis recurs at Grade 3 or higher despite corticosteroids permanently discontinue pembrolizumab.
 
If Grade 3 lasting >1 week despite oral prednisone, administer IV corticosteroids followed by high-dose oral corticosteroids per institutional standard.
 
Permanently discontinue pembrolizumab.

Grade 4	Permanently discontinue blinatumomab.	
Start prednisone 1-2 mg/kg oral daily with taper over at least 4 weeks after resolution to ≤ Grade 1. If Grade 3 lasting >1 week despite oral prednisone, administer IV corticosteroids followed by high-dose oral corticosteroids per institutional standard.
 
Permanently discontinue pembrolizumab.

*Patients requiring a delay of blinatumomab >14 days due to toxicity should go off protocol therapy.
		

Nephritis	Management for Blinatumomab	Management for Pembrolizumab
≤ Grade 1	No change in dose	No change in dose.
Grade 2	No change in dose	Withhold until ≤ Grade 1. Missed doses are not made up. Start prednisone 1-2 mg/kg oral daily with taper over at least 4 weeks after resolution to ≤ Grade 1. If nephritis recurs at Grade 2 or higher despite corticosteroids then permanently discontinue pembrolizumab.
Grade 3	Withhold* until resolved to ≤ Grade 1 then resume blinatumomab at 9 mcg/day. Escalate to 28 mcg/day after 7 days if the toxicity does not recur. If nephritis recurs then permanently discontinue blinatumomab.	Start prednisone 1-2 mg/kg oral daily with taper over at least 4 weeks after resolution to ≤ Grade 1. Permanently discontinue pembrolizumab.
Grade 4	Permanently discontinue blinatumomab.	Start prednisone 1-2 mg/kg oral daily with taper over at least 4 weeks after resolution to ≤ Grade 1. Permanently discontinue pembrolizumab.
*Patients requiring a delay of blinatumomab > 14 days due to toxicity should go off protocol therapy.		

Hypophysitis	Management for Blinatumomab	Management for Pembrolizumab
≤ Grade 1	No change in dose	No change in dose.
Grade 2	No change in dose	Withhold until ≤ Grade 1. Missed doses are not made up. Start prednisone 1-2 mg/kg oral daily with taper over at least 4 weeks after resolution to ≤ Grade 1. Replacement of appropriate hormones may be required as the steroid dose is tapered. If hypophysitis recurs at Grade 2 or higher despite corticosteroids then permanently discontinue pembrolizumab.
Grade 3	Withhold* until resolved to ≤ Grade	Give methylprednisolone 2 mg/kg

Hypophysitis	Management for Blinatumomab	Management for Pembrolizumab
	1 then resume blinatumomab at 9 mcg/day. Escalate to 28 mcg/day after 7 days if the toxicity does not recur. If hypophysitis recurs then permanently discontinue blinatumomab.	IV once then prednisone 1-2 mg/kg oral daily with taper over at least 4 weeks after resolution to \leq Grade 1. Replacement of appropriate hormones may be required as the steroid dose is tapered. Permanently discontinue pembrolizumab.
Grade 4	Permanently discontinue blinatumomab.	Give methylprednisolone 2 mg/kg IV once then prednisone 1-2 mg/kg oral daily with taper over at least 4 weeks after resolution to \leq Grade 1. Replacement of appropriate hormones may be required as the steroid dose is tapered. Permanently discontinue pembrolizumab.
*Patients requiring a delay of blinatumomab >14 days due to toxicity should go off protocol therapy.		

Immune-mediated hepatitis	Management for Blinatumomab	Management for Pembrolizumab
\leq Grade 1	No change in dose	No change in dose.
Grade 2	No change in dose	Withhold until \leq Grade 1. Missed doses are not made up. Start prednisone 1-2 mg/kg oral daily with taper over at least 4 weeks after resolution to \leq Grade 1. If immune-mediated hepatitis recurs at Grade 2 or higher despite corticosteroids then permanently discontinue pembrolizumab.
Grade 3	Withhold* until resolved to \leq Grade 1 then resume blinatumomab at 9 mcg/day. Escalate to 28 mcg/day after 7 days if the toxicity does not recur. If immune-mediated hepatitis recurs then permanently discontinue blinatumomab.	Give methylprednisolone 2 mg/kg IV once then prednisone 1-2 mg/kg oral daily with taper over at least 4 weeks after resolution to \leq Grade 1. Replacement of appropriate hormones may be required as the steroid dose is

Immune-mediated hepatitis	Management for Blinatumomab	Management for Pembrolizumab
		tapered. Permanently discontinue pembrolizumab.
Grade 4	Permanently discontinue blinatumomab.	Give methylprednisolone 2 mg/kg IV once then prednisone 1-2 mg/kg oral daily with taper over at least 4 weeks after resolution to \leq Grade 1. Replacement of appropriate hormones may be required as the steroid dose is tapered. Permanently discontinue pembrolizumab.
*Patients requiring a delay of blinatumomab > 14 days due to toxicity should go off protocol therapy.		

Type I Diabetes Mellitus Developing on Pembrolizumab	Management for Blinatumomab	Management for Pembrolizumab
\leq Grade 1	No change in dose	No change in dose.
Grade 2	No change in dose	No change in dose.
Grade 3	Withhold* until resolved to \leq Grade 1 then resume blinatumomab at 9 mcg/day. Escalate to 28 mcg/day after 7 days if the toxicity does not recur. If type I diabetes mellitus recurs then permanently discontinue blinatumomab.	Insulin replacement therapy is recommended for Type I diabetes mellitus and for Grade 3-4 hyperglycemia associated with metabolic acidosis or ketonuria. Evaluate patients with serum glucose and a metabolic panel, urine ketones, glycosylated hemoglobin, and C-peptide. Permanently discontinue pembrolizumab.
Grade 4	Permanently discontinue blinatumomab.	Insulin replacement therapy is recommended for Type I diabetes mellitus and for Grade 3-4 hyperglycemia associated with metabolic acidosis or ketonuria.

Type I Diabetes Mellitus Developing on Pembrolizumab	Management for Blinatumomab	Management for Pembrolizumab
		Evaluate patients with serum glucose and a metabolic panel, urine ketones, glycosylated hemoglobin, and C-peptide. Permanently discontinue pembrolizumab.
*Patients requiring a delay of blinatumomab > 14 days due to toxicity should go off protocol therapy.		

Immune-mediated hyperthyroidism	Management for Blinatumomab	Management for Pembrolizumab
≤ Grade 1	No change in dose	No change in dose
Grade 2	No change in dose	No change in dose Treat with non-selective beta-blockers (eg. Propranolol) and/or thionamides as appropriate Monitor for signs and symptoms of the disorders
Grade 3	Withhold* until resolved to ≤ Grade 1 then resume blinatumomab at 9 mcg/day. Escalate to 28 mcg/day after 7 days if the toxicity does not recur. If immune-mediated hyperthyroidism recurs then permanently discontinue blinatumomab.	Withhold of permanently discontinue pembrolizumab Treat with non-selective beta-blockers (eg. Propranolol) and/or thionamides as appropriate Monitor for signs and symptoms of the disorders
Grade 4	Permanently discontinue blinatumomab.	Withhold of permanently discontinue pembrolizumab Treat with non-selective beta-blockers (eg. Propranolol) and/or thionamides as appropriate Monitor for signs and symptoms of the disorders
*Patients requiring a delay of blinatumomab > 14 days due to toxicity should go off protocol therapy.		

Immune-mediated hypothyroidism	Management for Blinatumomab	Management for Pembrolizumab
≤ Grade 1	No change in dose	No change in dose
Grade 2	No change in dose	No Change in dose Initiate thyroid replacement hormones (eg, levothyroxine or liothyronine) per standard of care Monitor for signs and symptoms of thyroid disorders.
Grade 3	Withhold* until resolved to ≤ Grade 1 then resume blinatumomab at 9 mcg/day. Escalate to 28 mcg/day after 7 days if the toxicity does not recur. If immune-mediate hypothyroidism recurs then permanently discontinue blinatumomab.	No change in dose Initiate thyroid replacement hormones (eg, levothyroxine or liothyronine) per standard of care Monitor for signs and symptoms of thyroid disorders.
Grade 4	Permanently discontinue blinatumomab.	No change in dose Initiate thyroid replacement hormones (eg, levothyroxine or liothyronine) per standard of care Monitor for signs and symptoms of thyroid disorders.
*Patients requiring a delay of blinatumomab > 14 days due to toxicity should go off protocol therapy.		

Other Immune-mediated Adverse Reactions	Management for Blinatumomab	Management for Pembrolizumab
≤ Grade 1	No change in dose	No change in dose
Grade 2	No change in dose	Withhold until ≤ Grade 1. Missed doses are not made up. Start prednisone 1-2 mg/kg oral daily with taper over at least 4 weeks after resolution to ≤ Grade 1. If immune-mediated reaction recurs at Grade 2 or higher despite corticosteroids then permanently discontinue pembrolizumab.
Grade 3	Withhold* until resolved to ≤ Grade 1 then resume blinatumomab at 9	Give methylprednisolone 2 mg/kg IV once then prednisone 1-2

Other Immune-mediated Adverse Reactions	Management for Blinatumomab	Management for Pembrolizumab
	mcg/day. Escalate to 28 mcg/day after 7 days if the toxicity does not recur. If immune-mediate reaction recurs then permanently discontinue blinatumomab.	mg/kg oral daily with taper over at least 4 weeks after resolution to ≤ Grade 1. Permanently discontinue pembrolizumab.
